## LIST OF ABBREVIATIONS

Abbreviation or Specialist Term	Explanation
AE	adverse event
AESI	adverse event of special interest
ALP	alkaline phosphatase
ALT	alanine aminotransferase
ANCOVA	analysis of covariance
Apo	apolipoprotein
ApoA1	apolipoprotein A1
ApoB	apolipoprotein B
ApoCII	apolipoprotein CII
ApoCIII	apolipoprotein CIII
ApoE	apolipoprotein E
APRI	aspartate aminotransferase (AST) to platelet ratio index
AST	aspartate aminotransferase
ATC	Anatomical Therapeutic Chemical
AUC	area under the concentration-time curve
AUC 0-6	area under the concentration-time curve from hour 0 to last sampling time (hour 6)
AUDIT	Alcohol Use Disorders Identification Test
BARD	body mass index, aspartate aminotransferase to alanine aminotransferase ratio, and diabetes
BLQ	below the limit of quantitation
BMI	body mass index
C4	7 $\alpha$ -hydroxy-4-cholesten-3-one
CA	cholic acid
cAMP	cyclic adenosine monophosphate
CAP	controlled attenuation parameter
CDCA	chenodeoxycholic acid
CETP	cholesterol ester transfer protein
CI	confidence interval
CK-18-M30	cytokeratin-18 neoepitope M30
CK-18-M65	cytokeratin-18 neoepitope M65
cm	centimeter(s)

Abbreviation or Specialist Term	Explanation
C max	maximum plasma concentration
CMH	Cochran-Mantel-Haenszel
CRN	clinical research network
CRP	C-reactive protein
CS	clinically significant
CSR	clinical study report
CTCAE	common terminology criteria for adverse events
CV	coefficient of variation
DB	double-blind
DCA	deoxycholic acid
DOB	date of birth
DOIC	date of informed consent
eCRF	electronic case report form
ECG	Electrocardiogram
EE	efficacy evaluable
Eq	equivalents
FGF-19	fibroblast growth factor-19
FIB-4	Fibrosis-4
FRS	Framingham Risk Score
FXR	farnesoid X receptor
G	gram(s)
GGT	gamma-glutamyl transferase
glyco-CA	glycine 6 $\alpha$ -ethyl cholic acid
glyco-CDCA	glycine 6 $\alpha$ chenodeoxycholic acid
glyco-DCA	glycine 6 $\alpha$ -ethyl deoxycholic acid
glyco-LCA	glycine 6 $\alpha$ -ethyl lithocholic acid
glyco-OCA	glycine 6 $\alpha$ -ethyl chenodeoxycholic acid
glyco-UDCA	glycine 6 $\alpha$ -ethyl ursodeoxycholic acid
H	high/above the reference/normal range
HbA1c	hemoglobin-specific A1c fraction
HDL	high-density lipoprotein
HDLc	HDL cholesterol concentration
HDLs	HDL particle size
HDLpc	HDL particle concentration

Abbreviation or Specialist Term	Explanation
HOMA- $\beta$	homeostatic model assessment – beta-cell function
HOMA-IR	homeostatic model assessment – insulin resistance
hs-CRP	high-sensitivity C-reactive protein
In	inch(es)
IB	investigator's brochure
ICF	informed consent form
ICH	International Conference on Harmonization
IL-6	interleukin-6
INR	International Normalized Ratio
IQR	interquartile range
ITT	intent-to-treat
Kg	kilogram(s)
JT	Joncheere-Terpstra
KM	Kaplan-Meier
L	low/below the reference/normal range
Lb	pound(s)
LCA	lithocholic acid
LCAT	lecithin-cholesterol acyltransferase
LDL	low-density lipoprotein
LDLc	LDL cholesterol concentration
LDLs	LDL particle size
LDLpc	LDL particle concentration
LOCF	last observation carried forward
LLN	lower limit(s) of normal
LLOQ	lower limit of quantification
Lp(a)	lipoprotein(a)
LS	least squares
LTSE	long-term safety extension
MedDRA	Medical Dictionary for Regulatory Activities
Mg	milligram(s)
mL	milliliter
mol	mole(s)
MW	molecular weight
NAFLD	nonalcoholic fatty liver disease

Abbreviation or Specialist Term	Explanation
NAS	nonalcoholic fatty liver disease activity score
NASH	nonalcoholic steatohepatitis
ND	not determined
NFS	nonalcoholic fatty liver disease fibrosis score
ng	nanogram
NMR	nuclear magnetic resonance
NR	not reported
OCA	obeticholic acid
ODS	output delivery system
PCSK9	proprotein convertase subtilisin/kexin type 9
PD	Pharmacodynamic
PK	pharmacokinetic
PP	per protocol
QT	the time between the start of the Q wave and the end of the T wave
QTc	corrected measure between Q wave and T wave (in heart's electrical cycle)
QTcB	QT interval corrected by the Bazett's formula
QTcF	QT interval corrected by the Fridericia's formula
RR	time between two consecutive R waves
SAP	statistical analysis plan
SD	standard deviation
SE	standard error
SI	International System of Units
SMQ	standardized MedDRA query
SQRT	square root
tauro-CA	taurine 6 $\alpha$ -ethyl cholic acid
tauro-CDCA	taurine 6 $\alpha$ chenodeoxycholic acid
tauro-DCA	taurine 6 $\alpha$ -ethyl deoxycholic acid
tauro-LCA	taurine 6 $\alpha$ -ethyl lithocholic acid
tauro-OCA	taurine 6 $\alpha$ -ethyl chenodeoxycholic acid
tauro-UDCA	taurine 6 $\alpha$ -ethyl ursodeoxycholic acid
TE	transient elastography
TEAE	treatment-emergent adverse event
$t_{max}$	time to reach $C_{max}$

Abbreviation or Specialist Term	Explanation
TG	triglycerides
TNF- $\alpha$	tumor necrosis factor-alpha
UDCA	ursodeoxycholic acid
ULN	upper limit(s) of normal
VLDL	very low density lipoprotein
VLDLc	VLDL cholesterol concentration
VLDLpc	VLDL and chylomircron particle concentration
VLDLs	VLDL particle size
WADD	weighted average daily dose
WHODDE	World Health Organization Drug Dictionary Enhanced

## 1. INTRODUCTION

This document outlines the statistical methods to be implemented during the analyses of the double-blind (DB) data collected within the scope of Intercept Pharmaceuticals, Inc. (henceforth referred to as Intercept or the Sponsor) for Protocol 747-209 (A Phase 2, Randomized, Double-Blind, Placebo-Controlled Clinical Study Investigating the Effects of Obeticholic Acid and Atorvastatin Treatment on Lipoprotein Metabolism in Subjects with Nonalcoholic Steatohepatitis). The purpose of this statistical analysis plan (SAP) is to provide specific guidelines from which the analyses will proceed. Any deviations from these guidelines will be documented in the clinical study report (CSR). The scope of this plan includes the detailed specifications of the statistical analyses for the DB only. A separate SAP will be written for the long-term safety extension (LTSE) phase of the study. The analyses described in this plan are considered a priori, in that they have been defined prior to database lock of the DB. Post hoc analyses will be labeled as such on the outputs and identified in the CSR. Further details about study design and procedures can be found in the protocol.

## 2. STUDY OBJECTIVES

The DB primary objective is to evaluate the effect of obeticholic acid (OCA) on low-density lipoprotein (LDL) metabolism in subjects with biopsy-confirmed nonalcoholic steatohepatitis (NASH) and to assess the ability of atorvastatin to modulate this effect.

The DB secondary objectives are:

- To evaluate the safety and tolerability of OCA alone and in combination with atorvastatin therapy in subjects with biopsy-confirmed NASH.
- To evaluate the effect of OCA with and without atorvastatin therapy, on
  - High-density lipoprotein (HDL), very low-density lipoprotein (VLDL), triglycerides (TG), total cholesterol, and apolipoprotein (Apo) concentrations
  - Components of the reverse cholesterol transport pathway

The DB exploratory objectives are:

- To evaluate the effect of OCA on:
  - Liver biochemistry, inflammation, and apoptosis
  - Markers of glucose metabolism including C-peptide, insulin, fasting plasma glucose, hemoglobin-specific A1c fraction (HbA1c), homeostatic model assessment – beta-cell function (HOMA- $\beta$ ), and homeostatic model assessment – insulin resistance (HOMA-IR)
  - Anthropometric measures including height (measured at Screening Visit 1 only), weight, waist and hip circumference measurements, body mass index (BMI), and waist-to-hip ratio calculations
  - Cardiovascular risk scores (eg, Framingham Risk Score [FRS] and Reynolds score)

- To evaluate the pharmacokinetics (PK) and pharmacodynamics (PD) of OCA and its conjugates
- To evaluate the bioanalytical concentrations of atorvastatin and its metabolites
- To evaluate improvement in noninvasive-radiological assessment of fibrosis via transient elastography (TE; at sites where available)

### **3. STUDY ENDPOINTS**

#### **3.1. Primary Endpoints**

The DB primary endpoints are change and percentage change from Baseline to Week 16 in LDL cholesterol concentration (LDLc), particle size (LDLs), and particle concentration (LDLpc).

#### **3.2. Secondary Endpoints**

As defined in the protocol, the DB secondary endpoints are lipoprotein metabolism, reverse cholesterol transport, and safety and tolerability endpoints.

##### **3.2.1. Lipoprotein Metabolism Endpoints**

The secondary parameters related to lipoprotein metabolism include HDL cholesterol concentration (HDLc), particle size (HDLs) and particle concentration (HDLpc); VLDL cholesterol concentration (VLDLc), particle size (VLDLs), and VLDL and chylomicrons particle concentration (VLDLpc); TG and total cholesterol concentrations; and apolipoprotein A1 (ApoA1), apolipoprotein B (ApoB), apolipoprotein E (ApoE), apolipoprotein CII (ApoCII), apolipoprotein CIII (ApoCIII), lipoprotein(a) [Lp(a)], and proprotein convertase subtilisin/kexin type 9 (PCSK9) enzyme level concentrations.

For each of these parameters, the endpoints are:

- Observed values, change from Baseline, and percentage change from Baseline at each DB post-Baseline visit

##### **3.2.2. Reverse Cholesterol Transport Endpoints**

The secondary parameters related to reverse cholesterol metabolism include pre- $\beta$ 1 HDL concentration, macrophage cholesterol efflux, lecithin-cholesterol acyltransferase (LCAT) activity, cholesterol ester transfer protein (CETP) activity.

For each of these parameters, the endpoints are:

- Observed values, change from Baseline, and percentage change from Baseline at each DB post-Baseline visit

##### **3.2.3. Safety and Tolerability Endpoints**

The DB safety and tolerability endpoints include the following:

- Extent of exposure to OCA and Atorvastatin

- Incidence of Treatment-Emergent adverse events (TEAEs)
- Observed values and change from Baseline at each DB post-Baseline visit in quantitative clinical laboratory values for coagulation, hematology, and serum chemistry
- Shift tables (ie, low-normal-high at Baseline versus low-normal-high at each DB post-Baseline visit in a 3-by-3 contingency table) from Baseline to worst DB post-Baseline value, last DB post-Baseline value, and at each scheduled DB post-Baseline visit for quantitative hematology, coagulation, and serum chemistry
- Observed values and change from Baseline at each DB post-Baseline visit in vital signs (ie, body temperature, sitting heart rate, and respiratory rate). Note: blood pressure (sitting) is described below in [Section 3.3.6](#)
- Observed values at Baseline and each DB post-Baseline visit, and change from Baseline at each DB post-Baseline visit in electrocardiogram (ECG) parameters (time between 2 consecutive R waves [RR], heart rate, PR, QRS, the time from the start of the Q wave an T wave (in heart's electrical cycle) (QT), QT interval corrected by Bazett's formula (QTcB), and QT interval corrected by Fridericia's formula (QTcF))
- Categorical summaries of abnormal QTcF values (ie, > 450 msec, > 480 msec, and > 500 msec) and change from baseline values (> 30 msec and > 60 msec)

### 3.3. Exploratory Endpoints

As defined in the protocol, the DB exploratory endpoints are liver biochemistry and markers of liver function, markers of liver inflammation, markers of hepatic apoptosis and fibrosis, glycemic control, OCA pharmacokinetics (PK), atorvastatin bioanalytical concentrations, anthropometric measures, pharmacodynamics (PD), noninvasive radiological liver fibrosis measurements, and cardiovascular risk scores.

In addition, noninvasive scores of liver fibrosis including nonalcoholic fatty liver disease (NAFLD) fibrosis score (NFS) ([Angulo 2007](#)), fibrosis-4 (FIB-4) ([Shah 2009](#)), aspartate aminotransferase (AST) to platelet ratio index (APRI) ([Calès 2009](#)), and body mass index (BMI), AST to alanine aminotransferase (ALT) ratio, and diabetes (BARD) ([Harrison 2008](#)) will be computed based on Baseline characteristics and biochemistry values at scheduled visits.

#### 3.3.1. Liver Biochemistry and Markers of Liver Function

For the laboratory parameters albumin, alkaline phosphatase (ALP (isoenzymes)), ALT (isoenzymes), AST, total and direct bilirubin, gamma-glutamyl transferase (GGT), and INR (International Normalized Ratio), and platelets:

- Observed values, change from Baseline, and percentage change from Baseline at each DB post-Baseline visit
- Shift from Baseline to each DB post-Baseline visit

### **3.3.2. Markers of Liver Inflammation**

For the laboratory parameters interleukin (IL-6), high-sensitivity C-reactive protein (hs-CRP), and tumor necrosis factor-alpha (TNF- $\alpha$ ):

- Observed values, change from Baseline, and percentage change from Baseline at each DB post-Baseline visit

### **3.3.3. Markers for Hepatic Apoptosis and Fibrosis**

For the laboratory parameters cytokeratin-18 neoepitope M30 (CK-18-M30) and cytokeratin-18 neoepitope M65 (CK-18-M65):

- Observed values, change from Baseline, and percentage change from Baseline at each DB post-Baseline visit

For noninvasive scores of liver fibrosis NFS, FIB-4, and APRI:

- Observed values, change from Baseline, and percentage change from Baseline at each DB post-Baseline visit

For noninvasive score of liver fibrosis BARD:

- Shift from Baseline to each DB post-Baseline visit

### **3.3.4. Glycemic Control**

For the laboratory parameters fasting glucose, fasting insulin, C-peptide, HbA1c, HOMA- $\beta$ , and HOMA-IR.

- Observed values, change from Baseline, and percentage change from Baseline at each DB post-Baseline visit

### **3.3.5. OCA Pharmacokinetics Endpoints**

The OCA PK Population will be used for analysis of PK parameters, which include plasma OCA (parent) and its conjugates (glycine 6 $\alpha$ -ethyl chenodeoxycholic acid [glyco-OCA] taurine 6 $\alpha$ -ethyl chenodeoxycholic acid [tauro-OCA]), total OCA, and potentially other conjugates or metabolites not yet identified. PK analyses will utilize standard non-compartmental methods.

PK parameter estimates will be summarized by active treatment group using descriptive statistics. Only samples that have a confirmed fasting of at least 8 hours or more before their visit will be included in the analysis.

- The PK endpoints include the Day 1 and Week 16 plasma concentrations at all collection time points. Plasma PK parameters will include maximum plasma concentration [Cmax], time to reach Cmax [tmax], and area under the concentration-time curve from hour 0 to last sampling time (hour 6) [AUC0-6].
- OCA dose-normalized versions of Cmax, and AUC0-6 will be calculated for Day 1 and Week 16.
- Steady-state accumulation ratios based on Cmax (Rac Cmax) and AUC0-6 (Rac AUC0-6) will be calculated:

$$R_{ac} C_{max} = \text{Week 16 } C_{max} / \text{Day 1 } C_{max}$$

$$R_{ac} AUC_{0-6} = \text{Week 16 } AUC_{0-6} / \text{Day 1 } AUC_{0-6}$$

- Metabolite ratios based on  $C_{max}$  ( $MRC_{max}$ ) and  $AUC_{0-6}$  ( $MRAUC_{0-6}$ ) will be calculated:

$$MR C_{max} = (C_{max} \text{ conjugate or metabolite} / C_{max} \text{ parent}) \times (\text{molecular weight parent} / \text{molecular weight conjugate or metabolite})$$

$$MR AUC_{0-6} = (AUC_{0-6} \text{ conjugate or metabolite} / AUC_{0-6} \text{ parent}) \times (\text{molecular weight parent} / \text{molecular weight conjugate or metabolite})$$

### 3.3.6. Anthropometric Measures and Blood Pressure

Anthropometric measures include height (measured and recorded only at Screening Visit 1), body weight, waist and hip circumference measurements, BMI, and waist-to-hip ratio calculations. Blood pressure (sitting) will also be collected.

- Observed values, change from Baseline, and percentage change from Baseline at each DB post-Baseline visit

### 3.3.7. Pharmacodynamics

For 7 $\alpha$ -hydroxy-4-cholesten-3-one (C4) and fibroblast growth factor-19 (FGF-19), conjugated and unconjugated endogenous bile acids, and total bile acids:

- Observed values and change from Baseline at each DB post-Baseline visit

### 3.3.8. Noninvasive Radiological Liver Fibrosis Measurements

Noninvasive radiological methods to assess liver stiffness and steatosis will be conducted via transient elastography (TE) at selected centers where the devices are available.

- Observed liver stiffness values and change from Baseline at each DB post-Baseline visit
- Proportion of subjects with any reduction in liver stiffness value (kPa) at Week 16
- Observed controlled attenuation parameter (CAP) (dB/m) values and change from Baseline at each DB post-Baseline visit
- Both liver stiffness and CAP values are median values based on number of valid measurements

### 3.3.9. Cardiovascular Risk Scores

The cardiovascular risk scores include the Framingham Risk Score (FRS) and Reynolds score. Each score is derived from a subject's age, sex, smoking status, total cholesterol and HDL levels, and other factors including family history, BMI, ethnicity, and medications. Cardiovascular scores will be calculated at the time of data analysis.

- Observed values, change from Baseline, and percentage change from Baseline at each DB post-Baseline visit

### **3.3.10. Cardiovascular Markers of Risk**

The cardiovascular markers of risk scores include adiponectin, plasminogen activator inhibitor-1(PAI-1), and B-type natriuretic peptide (BNP).

- Observed values, change from Baseline, and percentage change from Baseline at each DB post-Baseline visit

## **4. STUDY DESIGN AND PLAN**

This is a Phase 2, double-blind, randomized, placebo-controlled, multicenter study, evaluating the effects of OCA, and the subsequent addition of statin therapy, on lipoprotein metabolism in subjects with NASH with fibrosis stage 1 to 4, but no evidence of hepatic decompensation, in the DB phase, followed by an open-label LTSE phase to evaluate long term safety and efficacy.

Approximately 80 subjects with histological evidence of definite or probable NASH, who meet all inclusion and none of the exclusion criteria will be enrolled in the study. The histological evidence of definite or probable NASH will be based on the central read of a liver biopsy obtained no more than 1 year prior to randomization and a nonalcoholic fatty liver disease activity score (NAS) of 4 or greater. Subjects not using statin therapy (ie, statin-free) and statin-treated subjects may be enrolled. Statin-treated subjects will be required to stop statin treatment (after signing informed consent) for up to 5 weeks, including a 4-week statin washout period, prior to Randomization/Day 1.

Subjects will have a screening period of up to 5 weeks prior to Randomization/Day 1. At the Randomization (Day 1) Visit, subjects will be randomized in a 1:1:1:1 ratio to receive OCA 5 mg, OCA 10 mg, OCA 25 mg, or placebo, orally, once daily, for 16 weeks. Randomization will be stratified by the pre-randomization fasting serum LDLc ( $\leq$ 125 mg/dL or  $>$ 125 mg/dL) and baseline fibrosis stage (stage 1, 2 or stage 3, 4).

[figure not shown]
Subjects will attend on-site clinic visits at Weeks 2, 4, 8, 12, and 16 and will be contacted at Weeks 6, 10 and 14 to assess safety and treatment compliance. At the Week 4 Visit, all subjects will initiate treatment with atorvastatin at a dose of 10 mg once daily. At the Week 8 Visit, atorvastatin will be increased to 20 mg once daily (if 10 mg daily is tolerated), and continued for an additional 4 weeks. After 4 weeks of treatment at 20 mg, the atorvastatin dose may be titrated (up or down) as clinically indicated. The final visit during the DB phase will occur at Week 16, after which subjects may continue into the open-label LTSE.

During the LTSE phase, all subjects will be treated with open-label OCA 10 mg or 25 mg. Subjects randomized to placebo or OCA 5 mg during the double-blind phase will be randomized in a 1:1 ratio to receive OCA 10 mg or OCA 25 mg upon entry into and throughout the LTSE phase. Subjects randomized to OCA 10 mg or OCA 25 mg during the double-blind phase will continue on the same dose throughout the LTSE. In the event of OCA-related tolerability concerns, the Investigator may refer to the Investigator's Brochure (IB) for possible treatment options. Subjects may continue, discontinue, or modify the atorvastatin therapy as clinically indicated. The LTSE will continue for approximately 2 years.

The overall study duration is up to 125 weeks including a Screening period of up to 5 weeks (depending on current statin use); a 16-week DB; and a 2-year, open-label LTSE.

A schematic of the study design is presented in Figure 1.

**Figure 1: Study Design Schematic**

LTSE: long-term safety extension; Wk = week

Note: Statin therapy refers to atorvastatin.

Δ = Telephone Safety Contact at Week 6, Week 10, and Week 14

## 5. DETERMINATION OF SAMPLE SIZE

It is the intent of this study to characterize the components of LDL metabolism (ie, LDLc, LDLs, and LDLpc) in subjects with NASH before and after treatment with OCA and to assess the changes induced by HMG Coenzyme A reductase inhibitor (atorvastatin) therapy. Assuming a 22 mg/dL increase from Baseline with a standard deviation of 24 in LDLc in the OCA 25 mg group without atorvastatin therapy after 16 weeks of treatment based on data from FXR Ligand OCA in NASH Treatment (FLINT) study, a sample size of 20 subjects per group will provide greater than 97.3% power to demonstrate the statistically significant difference of LDLc increase from Baseline with a 2-sided type I error of 0.05.

## 6. GENERAL ANALYSIS CONSIDERATIONS

### 6.1. Data Reporting

The statistical analyses will be reported using summary tables, figures, and data listings. All output will be incorporated into Microsoft Word rich text format (.rtf) files, sorted and labeled according to the ICH recommendations, and formatted to the appropriate page size(s).

Laboratory units will be summarized and presented in the International System of Units (SI) and conventional units.

Individual subject data obtained from the electronic case report forms (eCRFs), external laboratory data, and any derived data (such as change from Baseline and percent change from Baseline) will be presented in data listings by subject. Data from all assessments, whether scheduled or unscheduled, will be listed by subject and visit. Unscheduled visits and visits occurring more than one day outside protocol defined window will not be included in the table summaries, excluding transient elastography measurements

The analyses described in this plan are considered a priori, in that they have been defined prior to database lock of the DB. Post hoc analyses will be labeled as such on the outputs and identified in the CSR.

Analyses and tabulations will be performed using SAS® Version 9.3 or higher. PK parameters will be estimated using Phoenix® WinNonlin® Version 6.3 or higher. The following processes will be employed to validate statistical outputs: analysis datasets, summary tables, and data listings will be verified through independent programming; graphical displays will be compared against supporting summary tables; and all outputs will undergo a senior-level statistical review. The process includes confirmation that statistically valid methods have been implemented and that all data manipulations and calculations are appropriate and accurate. Checks will be made to ensure accuracy, adherence to this SAP, consistency within tables, and agreement between tables and their corresponding data listings. Upon completion of validation/verification and quality review procedures, all documentation will be collected and filed in the study master file by the project statistician or designee.

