## **11.6. Clinical Laboratory Evaluations**

Clinical laboratory evaluations during the DB are assessed at the central laboratory. The central laboratory reference/normal ranges will be used in determining whether a subject's value is above (H) or below (L) the reference/normal range. A listing of available laboratory reference/normal ranges for each laboratory parameter will be provided including age, sex, and values with units.

Quantitative hematology, coagulation, and serum chemistry laboratory parameters will be summarized by treatment group in SI and conventional units using arithmetic summary statistics as described in [Section 6.2.1](#) at Baseline and at each scheduled DB post-Baseline visit. Change from Baseline will also be summarized in the same manner. Re-tests or unscheduled visit results after first dose of investigational product in the DB will not be summarized but will be included in the data listings. Re-tests or unscheduled visit results prior to the administration time of the first dose in the DB will be included in the calculation of Baseline.

For laboratory test results that are below the quantifiable limits:

    Imputed laboratory result = (numeric portion of the result)  $\times$  0.9.

For laboratory test results that are above the quantifiable limits:

    Imputed laboratory result = (numeric portion of the result)  $\times$  1.1.

In addition, shift tables (ie, low-normal-high at Baseline versus low-normal-high at DB post-Baseline visit in a 3-by-3 contingency table) from Baseline to worst value, last value, and at each

scheduled DB post-Baseline visit will be provided for hematology, coagulation, and serum chemistry by treatment group. Worst post-Baseline value is defined as the most abnormal value.

Urinalysis results will not be summarized but will be provided in a data listing.

Listings of all laboratory values will flag values outside of the normal range as high (H) or low (L) and indicate whether or not a value is clinically significant (CS), based on Investigator judgment.

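### SAP Section 6.1 drops unscheduled and out-of-window results from all tables without exempting the worst-value and last-value laboratory shifts, so worst shifts can be under-reported

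*SAP*

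**What the plan says.** SAP Section 6.1 (Data Reporting) governs table content: "Unscheduled visits and visits occurring more than one day outside protocol defined window will not be included in the table summaries, excluding transient elastography measurements". Transient elastography is the only exemption. The same section keeps the full data in listings: "Data from all assessments, whether scheduled or unscheduled, will be listed by subject and visit".

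Section 3.2.3 (Safety and Tolerability Endpoints) makes laboratory shifts a safety endpoint, "from Baseline to worst DB post-Baseline value, last DB post-Baseline value, and at each scheduled DB post-Baseline visit". Section 11.6 (Clinical Laboratory Evaluations) repeats the plan for hematology, coagulation and serum chemistry, and adds: "Worst post-Baseline value is defined as the most abnormal value". Neither section says which results are eligible for the worst or the last value.

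At the end of its paragraph on by-visit summary statistics, Section 11.6 also says: "Re-tests or unscheduled visit results after first dose of investigational product in the DB will not be summarized". The shift tables come in a later paragraph.

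Appendix A lists the shift outputs as Tables 14.3.4.2.1 and 14.3.4.2.2 (hematology and coagulation) and 14.3.4.4.1 and 14.3.4.4.2 (serum chemistry), all for the Safety Population.

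**The concern.** A worst-value shift table is there to show how far each subject's laboratory result moved at its most extreme, whenever that was seen. Extreme results often surface in samples taken outside the visit schedule. If the general reporting rule removes those samples first, the table shows the worst of the in-window scheduled results, which is a narrower quantity than its definition promises. The last-value shift has a similar problem: when the final sample is unscheduled or out of window, an earlier result stands in for it.

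What is at stake is the tabulated safety summary. A reader of the study report who relies on the shift tables could see fewer abnormal shifts than the data contain. Two programmers could also follow the SAP in good faith and produce different tables.

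**Working it through.** The SAP states no figure to reproduce. The check is mainly a reading of the text, followed by simple arithmetic for scale.

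**1. Does the Section 6.1 rule reach the shift tables?** The rule applies to table summaries in general and is not limited to by-visit statistics. The shift outputs are numbered tables in Appendix A, so on its plain words the rule covers them.

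**2. Is there an exemption?** Sections 3.2.3, 6.1, 6.3.1, 6.3.2, 11.6 and 12 and Appendix A were read for one. The only post-dose exemption found is for transient elastography in Section 6.1.

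**3. What do the endpoint and analysis sections imply?** In both 3.2.3 and 11.6 the word *scheduled* is attached only to the by-visit shifts. The worst and last values carry no such limit. This points to an intention to use all post-dose results, but neither section says so, and neither sets the general rule aside.

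**4. Direction of the effect.** Let A be all of a subject's double-blind post-dose results for one parameter, and R the subset that Section 6.1 retains. Because R is contained in A, the most abnormal member of R is no more abnormal than the most abnormal member of A. Restriction can therefore lower a subject's worst category or leave it unchanged; it cannot raise it. The last value has no fixed direction, since the replacement may be better or worse than the true last result.

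**5. When it bites.** The worst-value table changes only if a subject has an unscheduled, re-test or out-of-window result in a more abnormal category than every retained result. The SAP gives no rate for this.

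**6. Scale per affected subject.**
- Subjects per arm: about 80 randomized 1:1:1:1 (Section 4), so 80 / 4 = 20. Section 5 agrees: "a sample size of 20 subjects per group".
- One affected subject: 1 / 20 = 5 percentage points of that arm's rate.
- Two affected subjects: 2 / 20 = 10 percentage points.

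These use the whole arm as denominator. With fewer evaluable subjects for a parameter, the step per subject is larger.

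**7. Outputs touched.** Two analyses × two unit systems = 4 tables.

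**The case against.** The strongest reply is that the SAP already means the right thing. The Section 11.6 sentence about re-tests and unscheduled results closes the paragraph on by-visit statistics, and the shift tables begin later. There, *scheduled* qualifies only the third kind of shift, and worst is defined without restriction. A specific definition can reasonably be taken to override a general reporting rule. Nothing is lost from the record either: all results are listed with high/low and clinical-significance flags, and abnormalities reported as adverse events enter those tables. Finally, re-tests are often prompted by an abnormal result, so restricting to scheduled samples keeps ascertainment more even across subjects and arms.

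Much of this stands. Section 11.6 should not be counted as a second, independent exclusion of the shifts, and the probable intention is to use all results. But the reply leaves Section 6.1 in place. That section is not confined to by-visit output, is the only source of the out-of-window exclusion, and names one exemption that is not this one. It also calls for checks of adherence to the SAP, which could favor the literal version.

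Four stronger readings are tempting but not supported:
- *That the SAP contradicts itself outright.* The sections can be reconciled; the rule is badly fixed rather than contradictory.
- *That Baseline and post-Baseline are treated inconsistently.* Section 11.6 does say "Re-tests or unscheduled visit results prior to the administration time of the first dose in the DB will be included in the calculation of Baseline", but this only applies the Section 6.3.1 definition of Baseline as the last pre-dose value.
- *That early-termination samples are lost.* Section 8.5 mentions that visit only for the AUDIT score. Whether laboratory samples are taken there, and how the visit is classed, belongs to the protocol, which is not at hand.
- *That a given share of results is lost, or that the last value falls back by a given time.* Section 4 says "Subjects will attend on-site clinic visits at Weeks 2, 4, 8, 12, and 16", but this is a list of visits, not a laboratory schedule. Such figures would assume a full panel at every visit.

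**Conclusion.** The point holds in a limited form. Section 6.1, followed literally, can remove the most abnormal or the latest laboratory result from the worst-value and last-value shift tables, and no text in the SAP prevents this. For worst values the error can only be under-reporting. Each affected subject is worth about 5 percentage points in an arm of about 20, assuming the arm is the denominator. How many subjects would be affected cannot be derived from the SAP, so no overall bias can be stated.

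A reader might infer that abnormal results would be concealed. That goes too far: they remain in the listings and, where reported as events, in the adverse event tables. The primary lipid endpoints do not depend on these tables. This should be clarified because it concerns a planned safety endpoint and two reasonable readings give different tables; it does not undermine the study.

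**What to change.** State in Section 6.1, with a cross-reference in 11.6, that the worst-value and last-value laboratory shifts use all double-blind post-dose results, including re-tests, unscheduled results and out-of-window results. State also that the exclusions in 6.1 and 11.6 apply, for laboratory data, only to by-visit summaries and by-visit shifts.

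The cost is a short text change in two sections and a small change to one derivation; the data are already held for the listings. The downside is uneven ascertainment, because a subject sampled more often has more chances to record an abnormal value. A footnote to the four shift tables should say so.
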